## 9.2 Treatment Selection Factors

Patient treatment will be selected by tumor ATRX and/or 1p/19q chromosomal status and by tumor PI3K/mTOR pathway activation (Pathact) as determined by immunohistochemistry for phospho-PRAS40 (see Section 7.3.2 for details).

## 9.3 Determination of Sample Size and Accrual Rate

Documentation of prognosis among LGG patients treated with TMZ is limited in the published literature. A recent study was conducted to assess whether IDH1 or IDH2 mutations predict longer survival in LGG patients (Houillier, Wang et al. 2010). In this study, it was reported that the median PFS among LGG patients whose tumors were 1p-19q co-deleted and IDH mutated was 37.9 months while it was 32.9 months for the patients whose tumors were 1p-19q intact and IDH mutated.

**Arm 1:** As we expect patients with LGGs that are IDH-mutated with ATRX loss and/or 1p/19q chromosomes intact, and with PI3K/mTOR pathway activated (Pathact) treated with everolimus to have better prognosis than if treated with TMZ alone, we consider the lower threshold for the probability of 33-month PFS to be 50%. If the true PFS-33 proportion is 70%, with 35 patients we will have 86% confidence in the PFS-33 estimate with a one-tailed 90% confidence interval.

**Arm 2:** Similarly, we expect patients with LGGs that are IDH-mutated with ATRX loss and/or 1p/19q chromosomes intact, and with PI3K/mTOR pathway non-activated (Pathnon-act) treated with the combination of everolimus and TMZ to have better prognosis than if treated solely with TMZ, we again consider the lower threshold for the probability of 33-month PFS to be 50%. If the true PFS-33 proportion is 70%, with 35 patients we will have 86% confidence in the PFS-33 estimate with a one-tailed 90% confidence interval.

**Arm 3:** We expect patients with ATRX intact and/or 1p-19q co-deleted (regardless of PI3K/mTOR pathway status) LGGs treated with everolimus to have better prognosis than if treated with TMZ alone. Therefore, we consider the lower threshold for the probability of 38-month PFS to be 50%. If the true PFS-38 proportion is 70%, with 35 patients we will have 86% confidence in the PFS-38 estimate with a one-tailed 90% confidence interval.

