**Figure 2-1: Study Schema**

## 5 Population

The total number of patients enrolled in this study will be 105, with 35 patients in each of the three treatment arms.

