## 9.4 Stopping Rules

If the discontinuation rate due to toxicity is 20% or greater and the lower bound for the one-tailed 95% confidence interval is > 10%, this strategy would not be considered feasible. Six months after the 20th patient is enrolled and six months after the 40th patient is enrolled, we will assess the frequency of toxicity requiring permanent discontinuation of the drug. If there is a greater than 20% rate for discontinuation of drug due to toxicity during therapy at either time point, the study accrual will be suspended and we will assess the study design. Because the confidence interval may be calculated multiple times, the actual confidence level will be overstated. This increases the likelihood of rejecting the therapy due to toxicity. However, this is felt to be an acceptable risk in order to prevent continuation of a therapy that may have a toxicity rate that precludes its routine use.

If there is any treatment-related mortality event, the study accrual will be suspended until all data pertaining to the event is reviewed by the Study Chair and co-investigators.

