### 9.5.2 Analysis of Primary Endpoints

**33-(38-)month PFS:** Analyses will be performed after all enrolled patients have completed 33 (38) months on study, or whenever the progression status of all patients has been established, whichever comes first. The primary analysis will be based on Kaplan-Meier method. Kaplan-Meier estimates and the associated 95% CIs will be calculated for the 33-(38-)month PFS separately for the three arms. The Cox proportional hazards model will also be used to allow for adjustment of the prognostic factors including age, KPS, and extent of resection.

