### 9.5.3 Analysis of Secondary Endpoints

Overall survival and objective response and seizure rate: The method described above for the analysis of PFS-33 and PFS-38 will be applied to the analysis of OS. Response is based on the best response, defined as the best objective status as assessed by the RANO criteria. The point estimate and the associated 2-sided 95% CI for both the response rate and the seizure rate will be calculated separately for the three arms. To assess the reduction in seizure rate we will compare the seizure rate on study to that experienced one month prior to enrolling in the study. We will follow the RANO LGG guideline (van den Bent, Wefel, et al 2011) which calls a 50% or more reduction number of monthly seizures an ‘improvement’; a 50% or more increase a ‘worsening’; and anything less than 50% in either direction a ‘stable seizure rate’.

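### The 86% in section 9.3 is the power of a one-sided 90% limit against 50% PFS, but section 9.5.2 names only 95% CIs and no threshold; if those CIs decide, power is 65% or 77% under most readings

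*Combined protocol and SAP*

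**What the plan says.** Section 5 sets the size: "The total number of patients enrolled in this study will be 105, with 35 patients in each of the three treatment arms".

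Section 9.3 gives the same reasoning for each arm. The lower threshold for PFS at the landmark (33 months in Arms 1 and 2, 38 months in Arm 3) is 50% and the assumed true rate is 70%. For Arms 1 and 2 it concludes that "with 35 patients we will have 86% confidence in the PFS-33 estimate with a one-tailed 90% confidence interval"; Arm 3 has the same sentence for PFS-38.

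Section 9.5 adds the endpoints, an intention-to-treat basis, and timing once landmark status is known for every patient. The method is in section 9.5.2: "The primary analysis will be based on Kaplan-Meier method", and "Kaplan-Meier estimates and the associated 95% CIs will be calculated for the 33-(38-)month PFS separately for the three arms". A Cox model adjusted for prognostic factors is added. No level other than 95%, no side, no interval method, no threshold and no success criterion appears there.

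Elsewhere the plan is more explicit. The toxicity rule in section 9.4 gives a level, a side and a cut-off: "the lower bound for the one-tailed 95% confidence interval is > 10" per cent. Section 9.5.3 states the side for the secondary endpoints: "The point estimate and the associated 2-sided 95% CI for both the response rate and the seizure rate".

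**The concern.** The operating figure that justifies 35 patients per arm belongs to one interval (one-sided 90%, compared with 50%). The only interval named for the primary analysis is another one (95%, side unstated, compared with nothing). No text connects the two, so the plan does not say how an arm will be judged against 50%.

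An arm with 22 of 35 progression-free would clear the threshold implied by section 9.3 and would miss it under nearly every reading of section 9.5.2. At 23 of 35 the result depends on side and transform, neither of which is stated. These are separate, uncontrolled arms, so the comparison with a fixed 50% is the only yardstick, and it should be settled before the data are seen. The word *confidence* in section 9.3 adds to the difficulty: a reader cannot tell from the text that 86% is the probability of a positive result at a true rate of 70%.

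**Working it through.** **Inputs.** n = 35 per arm (sections 5 and 9.3); threshold 50% and true rate 70% (section 9.3); one-sided 90% limit (section 9.3); 95% CI (section 9.5.2). Section 9.5 times the analysis for when landmark status is known for all patients, so I assume no censoring before the landmark. The Kaplan-Meier estimate is then s = x/35, and Greenwood's variance equals the binomial variance s(1 − s)/35.

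**Rule.** An arm succeeds if its lower confidence limit exceeds 0.50. Let k be the smallest count x for which this happens. Type I error is P(X ≥ k | 0.5) and power is P(X ≥ k | 0.7), with X binomial (35, p):

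| k | Type I error | Power |
|---|---|---|
| 21 | 0.1553 | 0.9269 |
| 22 | 0.0877 | 0.8650 |
| 23 | 0.0448 | 0.7729 |
| 24 | 0.0205 | 0.6516 |

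**Lower limits.** z = 1.282 for one-sided 90%, 1.645 for one-sided 95%, 1.960 for two-sided 95%.

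- Plain: s − z√[s(1 − s)/n]
- Log: s·exp{−z√[(1 − s)/(ns)]}
- Log-log: s raised to the power exp{z√[(1 − s)/(ns)]/|ln s|}
- Logit and arcsine: the usual transformed limits
- Clopper-Pearson: the beta quantile with parameters x and n − x + 1

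**Reproducing the 86%.** At 22/35, s = 0.6286 and its standard error is 0.0817. The plain one-sided 90% limit is 0.6286 − 1.282 × 0.0817 = 0.524. Clopper-Pearson gives 0.506 and log-log 0.514. At 21/35 these three are 0.494, 0.478 and 0.486, so the cut is 22, with power 86.5% and type I error 8.8%. Logit and arcsine give the same cut. The log transform is the exception: its limit at 21/35 is 0.503, so the cut is 21, power 92.7% and type I error 15.5%.

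**If the 95% CI decides.** Lower limits around the cut:

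| Limit | Clopper-Pearson | Plain | Log-log | Logit | Arcsine | Log |
|---|---|---|---|---|---|---|
| Two-sided 95%, 23/35 | 0.478 | 0.4999 | 0.476 | 0.488 | 0.494 | 0.517 |
| Two-sided 95%, 24/35 | 0.507 | 0.532 | 0.505 | 0.517 | 0.525 | 0.548 |
| One-sided 95%, 22/35 | 0.476 | 0.494 | 0.479 | 0.488 | 0.491 | 0.508 |
| One-sided 95%, 23/35 | 0.504 | 0.525 | 0.508 | 0.516 | 0.521 | 0.538 |

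The resulting designs:

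| Reading | Cut | Type I error | Power |
|---|---|---|---|
| Section 9.3, one-sided 90% (all but log) | 22/35 | 8.8% | 86.5% |
| Two-sided 95%, five methods other than log | 24/35 | 2.0% | 65.2% |
| Two-sided 95%, log | 23/35 | 4.5% | 77.3% |
| One-sided 95%, five methods other than log | 23/35 | 4.5% | 77.3% |
| One-sided 95%, log | 22/35 | 8.8% | 86.5% |

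**How often it matters.** If true PFS is 70%, P(X = 22) = 0.8650 − 0.7729 = 0.092, and P(X = 22 or 23) = 0.8650 − 0.6516 = 0.213 per arm.

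**The case against.** The strongest reply is that nothing is contradicted. Section 9.3 writes down in advance a sample size, a threshold, a side and a level that fit together and reproduce the 86%. Section 9.5.2 says only that 95% CIs will be calculated, which is reporting language with no decision attached. The objectives in section 3 are also worded as assessing PFS, not testing it. On that reading the section 9.3 limit is the criterion, the 95% CIs are descriptive, and no power is lost.

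That reading is possible, and under it the 86% stands. But the documents do not state it. Section 9.3 describes the properties of an interval without saying that an arm will be declared successful on it, and section 9.5.2 makes the 95% CIs part of the primary analysis without calling them descriptive. A 50% threshold and a 70% alternative imply a comparison, so pure estimation does not explain section 9.3 either.

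Two narrower points stand. First, moving from the 22/35 cut to a 95% limit is never more lenient, so that move cannot rescue an arm that failed at 22. The lenient openings are choosing the side or transform within the 95% readings, and using a log transform at the 90% level, where 21/35 would pass. Second, the cuts assume no censoring before the landmark. Section 9.1 censors at last contact, so with losses a count out of 35 no longer fixes the Kaplan-Meier limit and the cuts become illustrative. Neither point supplies the missing link.

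**Conclusion.** The concern holds as a mismatch between design and analysis. The 86% is correct as the exact power (86.5%, type I error 8.8%) of a one-sided 90% lower limit against 50%, but it is mislabelled, and it does not describe the one interval the primary analysis names. If that interval decides, power falls by about 21 points (86.5 − 65.2) when two-sided, or about 9 points (86.5 − 77.3) when one-sided, for every method examined except the log transform. With the log transform the figures are 77.3% and 86.5%.

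The lower figures are conditional on the 95% CI being used for the decision, on exact binomial calculation with n = 35, and on no censoring before 33 or 38 months. The sample size itself is not shown to be wrong. The plan should be corrected on this point before analysis.

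**What to change.** In section 9.5.2, state that the primary decision for each arm is whether the one-sided 90% lower confidence limit for PFS-33 (PFS-38 in Arm 3) exceeds 50%. Name the interval method: a log-log Kaplan-Meier limit keeps the cut at 22/35, whereas a log transform would lower it to 21/35 and raise type I error to 15.5%. Label the 95% CI as two-sided and descriptive.

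In section 9.3, replace the reference to 86% confidence with 86% power and an exact one-sided type I error of 8.8%.

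If the sponsor prefers the 95% CI to decide, section 9.5.2 should give its side and transform, and section 9.3 should restate the power to match: 65% for a two-sided log-log interval, or 77% for a two-sided log or one-sided log-log interval.

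The cost is wording in two sections, with no added patients, visits or follow-up. Only the second option has a further price: a less favourable stated power.

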#### Inclusion criteria:

1. Age  $\geq$  18 years
2. KPS  $\geq$  60
3. Adequate bone marrow function as shown by: ANC  $\geq$  1.5  $\times$  10^9/L, Platelets  $\geq$  100  $\times$  10^9/L, Hb  $\geq$  9.0 g/dL;
4. Adequate liver function as shown by:
  - a. Total serum bilirubin  $\leq$  2.0 mg/dL,

- b. ALT and AST  $\leq$  2.5x ULN,
- c. INR  $\leq$  2;
- 5. Adequate renal function: serum creatinine  $\leq$  1.5 x ULN;
- 6. Fasting serum cholesterol  $\leq$  300 mg/dL OR  $\leq$  7.75 mmol/L AND fasting triglycerides  $\leq$  2.5x ULN. NOTE: In case one or both of these thresholds are exceeded, the patient can only be included after initiation of appropriate lipid lowering medication with confirmed reduction of lab values to within eligibility parameters;
- 7. Signed informed consent obtained prior to any screening procedures.
- 8. Patients must have histologically proven supratentorial low-grade glioma at initial diagnosis and at the time of any subsequent surgeries; pathology must have been reviewed by UCSF neuropathology. Eligible low-grade gliomas include: astrocytoma, oligodendrogloma and mixed oligoastrocytoma. Pilocytic astrocytomas are excluded.
- 9. Patient's tumor must have documentation of the presence of an IDH-1 and/or IDH-2 mutation of any type.
- 10. Results of ATRX and/or 1p/19q chromosomal status: if ATRX is lost, 1p/19q status is not required. If ATRX is intact, 1p/19q chromosomal status must be available to permit treatment selection.
- 11. Results of pRAS40 testing.
- 12. Patients must have evaluable disease. Patients must begin treatment within 120 days of most recent surgical procedure.

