### **7.3.2 Treatment Selection Factors**

Patient treatment will be selected by 1p/19q chromosomal status as determined by fluorescence in-situ hybridization (FISH) and/or ATRX mutation as determined by immunohistochemistry. Briefly, deletion of 1p and 19q will be determined based on the determination of the ratio of test probe to reference probe. A deletion is defined as a ratio of test probe to reference probe <0.8 and >15% of the cells showing a reference:target ratio of at least 2:1. Patients whose tumor is 1p/19q intact will be further selected by tumor PI3K/mTOR pathway activation (Pathact) as determined by immunohistochemistry for phospho-PRAS40. Pathway activation will be defined as a score of greater than or equal to 1 based on an assessment of tumor cells immunopositive for phospho-PRAS40 as follows: 0, no significant positive staining in tumor cells; 1, 1-33% of tumor cells positive; 2, 33-66% positive; 3, greater than 66% tumors cells positive. A similar scoring system was used previously to assess pathway activation in low grade glioma [McBride et al. 2010]. Based on this study which identified 18 of 35 patients with p-PRAS40-positive tumors, we anticipate approximately 50% of newly diagnosed low-grade gliomas will be Pathact regardless of 1p/19q status.

The ATRX mutation typically results in a truncated protein and abrogated protein expression [Heaphy CM 2012; Liu XY 2012]. Thus, immunohistochemistry for ATRX can be performed and loss of immunostaining can be used as a surrogate for detecting ATRX mutations. For the evaluation of ATRX immunohistochemistry, only nuclear staining is assessed. A tumor is considered to be ATRX mutant when there is loss of ATRX in all tumor cell nuclei while nuclear positivity is present in non-neoplastic cells, including blood vessels, microglia, reactive astrocytes, and entrapped neurons. This assay will be performed clinically in a CLIA-certified laboratory, interpreted by a board-certified neuropathologist, and reported in the clinical chart.

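### Does one 50% PFS-33 benchmark, not split by p-PRAS40 status, call for a combined estimate of Arms 1 and 2?

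*Combined protocol and SAP*

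**What the plan says.** Section 9.3 cites a published TMZ-treated series and reports that median PFS was 37.9 months with 1p/19q co-deletion and IDH mutation, and that "it was 32.9 months for the patients whose tumors were 1p-19q intact and IDH mutated". For Arms 1 and 2 it turns the second figure into a 50% reference at 33 months. Arm 1 is given 50%, and for Arm 2 the text says "we again consider the lower threshold for the probability of 33-month PFS to be 50" per cent. The expectation for Arm 2 is for patients "to have better prognosis than if treated solely with TMZ", and the Arm 1 text makes the equivalent claim.

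Arms 1 and 2 are the two halves of one molecular group (ATRX lost and/or 1p/19q intact), divided by p-PRAS40 staining. Section 7.3.2 expects an even division, from a study "which identified 18 of 35 patients with p-PRAS40-positive tumors, we anticipate approximately 50% of newly diagnosed low-grade gliomas" to be activated. Section 5 plans 105 patients, "with 35 patients in each of the three treatment arms". Section 5.1 makes "Results of pRAS40 testing" an entry requirement.

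Under Section 9.5.2, Kaplan-Meier estimates with 95% intervals "will be calculated for the 33-(38-)month PFS separately for the three arms". A Cox model is added for "adjustment of the prognostic factors including age, KPS, and extent of resection". Pathway status is not on that list, and no PFS-33 estimate for Arms 1 and 2 together is planned. Section 3 states a separate primary objective for each arm.

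**The concern.** The reference population was not, as far as its description goes, divided by pathway status, but the trial population is. The protocol treats p-PRAS40 as a marker of poor outcome in patients not given signalling inhibitors. Section 1.2.1.2 reports a survival trend (P = 0.077) and Section 2.1 reports worse PFS (log-rank p = 0.07). If the same held under TMZ, the TMZ-alone reference would lie above 50% in Arm 2 and below 50% in Arm 1. Arm 2 could then clear its bar with no treatment gain, and Arm 1 could miss its bar despite one.

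No covariate adjustment removes this. Pathway status is constant within each of the two arms, and across them it coincides with regimen. Take Arm 2 at 25/35 (one-sided 90% lower bound 59%) and Arm 1 at 14/35 (29%). This looks like a working combination and an inactive monotherapy, but a prognostic marker could produce the same pattern. Since the 50% describes the undivided group, it is natural to ask for one supportive estimate over both arms: here 39/70 = 56%, lower bound 47%.

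**Working it through.** **Inputs.** Median 32.9 months, reference 50%, alternative 70%, 35 patients per arm, one-sided 90% interval and a stated 86% (all Section 9.3); 18 of 35 positive, about 50% (Section 7.3.2). Two inputs are assumptions because the documents do not give them: the hazard ratio (HR) of p-PRAS40 positive against negative under TMZ, and the positive share w in the benchmark series. PFS-33 is treated as binomial, ignoring censoring before 33 months.

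**1. Origin of the 50%.** With exponential PFS, 0.5^(33/32.9) = 0.499. The 50% is the published median restated.

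**2. The plan's own figure.** The Clopper-Pearson one-sided 90% lower bound is 0.478 at 21/35 and 0.506 at 22/35, so clearing 50% needs at least 22/35. This rule is inferred; the plan does not state it. P(X ≥ 22 | n = 35, p = 0.5) = 0.088 and P(X ≥ 22 | n = 35, p = 0.7) = 0.865, which reproduces the stated 86%.

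**3. Size of the effect, if there is one.** Let s be the TMZ-alone PFS-33 in pathway-negative patients and s^HR that in positive patients. Solve (1 − w)·s + w·s^HR = 0.5 with w = 0.5. The last three columns give the chance of clearing 50% when neither arm improves on TMZ alone. The combined rule is at least 41/70 (lower bound 0.502; 0.488 at 40/70).

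| HR (assumed) | Reference Arm 1 / Arm 2 | Arm 1 clears | Arm 2 clears | Combined clears |
|---|---|---|---|---|
| 1 | 0.500 / 0.500 | 8.8% | 8.8% | 9.4% |
| 1.5 | 0.430 / 0.570 | 1.4% | 30% | 9.2% |
| 2 | 0.382 / 0.618 | 0.3% | 52% | 8.8% |
| 3.58 | 0.291 / 0.709 | <0.1% | 89% | 7.4% |

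**4. What the documents say about HR.** They give none. Working back from p = 0.07 (z = 1.812), with se = 1/√(d × 18/35 × 17/35) for d events:

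- d = 35: HR 1.85 (95% CI 0.95 to 3.58)
- d = 20: HR 2.25 (0.94 to 5.41)
- d = 15: HR 2.55 (0.93 to 7.02)

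The event counts and the 18:17 split are assumptions, and every interval contains 1. The last row of the table is the upper limit of the first of these intervals.

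**5. What the combined estimate would add.**

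- Only Arm 1 works: HR 2, Arm 1 raised 20 points to 0.582, Arm 2 unchanged at its TMZ-alone 0.618. The combined estimate clears in 65%, and Arm 2 and the combined estimate both clear in 45%. A combination with no gain would appear to be supported.
- Only Arm 2 works: Arm 2 at 70%, Arm 1 at 50%, no marker effect. The combined estimate again clears in 65%, the same as in the opposite situation, and in the remaining 35% it would count against a regimen that works.
- Different share: enrolment is fixed at 35 + 35, so an unweighted pool is always 50:50. At HR 2 its error is 3.8% if the benchmark share is 40% and 17% if it is 60%, against a nominal 10%.

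**The case for a change.** The strongest case for a change is that the mismatch is real on the face of Section 9.3, that the sponsor's own rationale treats p-PRAS40 as prognostic, and that the remedy is cheap. Unlike Arm 2 alone, the combined error stays between 7.4% and 9.4% for every HR in the table, so it needs no knowledge of the HR. It uses a marker already required at entry, and fixing it in advance is better than pooling after the results are seen. If both arms truly reach 70%, it clears in 98%.

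The mismatch and the arithmetic stand. The inference that a change is needed does not. The stable error belongs to a different statement, that the split population as a whole does no better than TMZ. It does nothing for the claim about Arm 2, whose 52% at HR 2 is the same with or without the extra estimate. Nor can the pool separate a marker effect from a regimen effect: in the 25/35 and 14/35 example, 39/70 fits either explanation. Its stability also depends on the benchmark series having a similar positive share, which the documents do not give. Weighting by screening shares would need marker results from screened patients who were not enrolled, and no section plans to collect these for analysis. The pooled wording in Section 9.5.4 concerns exploratory mutation associations and is no precedent for a pooled PFS-33.

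**Conclusion.** No change to the plan. The observation is accurate: one benchmark, described by 1p/19q and IDH status only, serves two arms defined by p-PRAS40. Whether that biases either comparison depends on a prognostic effect under TMZ that the documents suggest only through two non-significant trends, neither from a series described as TMZ-treated. At HR 1 nothing is wrong, and the 86% is reproduced as stated. At HR 1.5 to 2 an Arm 2 with no gain over TMZ would clear 50% in 30% to 52% of trials, and Arm 1 in 1.4% to 0.3%. The documents cannot say where in that range the truth lies.

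Using one historical figure for both arms is a fair trade-off when no pathway-specific figure is cited. Section 9.3 already concedes that the literature on TMZ-treated patients is limited, the objectives are arm by arm, and no formal contrast of Arm 1 with Arm 2 is planned. A combined estimate would be an optional description. It corrects neither arm's comparison and should not be offered as support for either regimen. A sensible analyst would say, when reporting, that the 50% is not pathway-specific and that each arm's position against it, and any informal contrast of the two arms, needs caution. This conclusion rests on the binomial approximation, the inferred 22/35 rule, and the benchmark series being unsplit by pathway, which is read from its description because the source was not available.
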